17. DATA ANALYSIS PLAN

Descriptive statistics will be used to evaluate the rates related to the primary endpoint and health care utilization and HF hospitalization secondary endpoints for each group in the study population. Further, mean quality of life AFEQT scores will also be reported. General linear models will be used to identify factors associated with the risk of both AF burden and recurrent endpoints during follow-up.

For the primary endpoint of AF burden, defined as percentage of time spent in AF (i.e. **amount of time spent in AF divided by the total amount of time a patient was monitored**), the student's t-test will be used to statistically compare the placebo group vs. the active treatment group. This approach is subject to an examination of the distribution of the percent time in AF.

Currently, patients with persistent AF account for >60% of the AF ablation volume in each of the enrolling sites and therefore we anticipate a higher burden of AF than what has been reported in patients with paroxysmal AF, including CAPTAF (in which patients with paroxysmal AF)

comprised 70% of the study population).⁴²

Our preliminary data on 125 patients implanted with an ICM at URMC of whom 65% had persistent AF, show an overall AF burden of 25%. Other published studies have shown a higher burden of AF in persistent AF populations.⁴³ In the present study, enrollment will use a stratified proportionate allocation in a 2:1 ratio by type of AF (persistent vs. paroxysmal, respectively) to ensure a sufficient proportion of subjects with persistent AF.

Sample size

Our re-estimated power calculations are based on the following parameters:

- 1. 25 subjects randomized
- 2. Minimum follow-up of 6 months, average follow-up of 9 months.
- 3. Our preliminary interrogations suggest that we may have underestimated AF burden (possibly due to the higher risk characteristics of enrolled patients with heart failure, diabetes, and renal dysfunction). The revised AF burden estimate takes a conservative measure of at least 40%.

The Table below provides power calculations for a treatment effect in the range of 40% to 50%.

			SD		sample		total
	Average AF	Average AF					
	burden:	burden:					
Reduce	placebo	Intervention	deviation	power	size	dropout	sample
50%	40%	20.0%	15%	85%	23	10%	25
45%	40%	22.0%	15%	76%	23	10%	25
4370	4070	22.070	1370	/0/0	25	1070	23
43%	40%	22.8%	15%	73%	23	10%	25
40%	40%	24.0%	15%	66%	23	10%	25

Based on our preliminary interrogation data above, the primary outcome of AF burden over an average follow-up of 9 months is assumed to be 40% in the placebo group and 20-24% in the intervention (dapagliflozin) group, with a standard deviation of 15% (a conservative estimate which allows for 10% drop-out). With a sample of 25 subjects randomized, a reduction from 40% to 20%-22% would provide 85%-76% power, respectively. Other possible scenarios are provided in the Table above.

We therefore, believe that the study may be the first to provide pilot prospective data on the possible antiarrhythmic properties of dapagliflozin following AF ablation.

The study power should not be affected by the association of diabetic status and cardiovascular medications with the study drug, Dapagliflozin, or AF burden, the primary outcome of the study. Further, prior publications have not shown differential effects of this drug within diabetic status or medication subgroups. Also, because the study drug and placebo groups will be randomly

assigned the distribution of diabetic patients and use of cardiovascular medications should be similar in the two. We will perform a sensitivity analysis where we adjust for diabetics and heart failure both parametrically and non-parametrically. Finally, the study was not designed to be powered to look for affects in subgroups of the study population, only in the overall enrolled study group.

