4. STUDY DESIGN

The study is a randomized placebo-controlled prospective multicenter clinical trial of symptomatic AF potential subjects who are scheduled to undergo catheter ablation of AF. Prior to undergoing ablation, potential subjects will be enrolled (consented) into the study. Following successful ablation, study subjects will be randomized in a 1:1 ratio to treatment with dapagliflozin (10 mg daily) versus placebo. Prior to randomization the subject must have had the AF catheter ablation and an implanted functional CIED in place as described below.

AF burden will be monitored by a CIED) either, 1) ICM, used as standard of care (SOC) for AF management or 2) existing PPM, ICD, or CRT-D that has remote monitoring capabilities.

Enrolled subjects will be followed for a minimum duration of 6 months and a maximum duration of 12 months following randomization in both the dapagliflozin and placebo arms as follows:

- CIED interrogation to quantitate AF burden will be performed during in office visits and during remote device interrogations. Interrogation results (PHI redacted by enrolling site) will be shared with the study coordination and database center (CDC) at the University of Rochester where it will be further reviewed by an independent study arrhythmia adjudication committee. AF burden will be quantified.
- Clinical data on medication, cardiovascular events, quality of life, and subject reported outcomes, will be collected at standard clinical visits.

Primary Endpoint

AF burden assessed at the final follow-up visit following catheter ablation of AF, defined as percentage of time spent in AF (i.e. amount of time spent in AF divided by the total amount of time a subject was monitored).

[figure not shown]
Secondary Endpoints

- 1. Rate of health care utilization (recurrent hospitalizations, unplanned office visits, unplanned remote visits, need for emergency room visits)
- 2. Post-ablation HF hospitalization
- 3. AF burden and impact on quality of life measured using the AFEQT score.

Tertiary (exploratory) Endpoints

We will acquire data on the effect of dapagliflozin treatment on clinical outcomes in diabetic and non-diabetic subjects with AF. Accordingly, the following exploratory outcomes will be compared between the two groups:

- 1. Other cardiovascular events such as stroke and myocardial infarction

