- 2. Association of AF burden and AF type (paroxysmal vs persistent) with clinical decompensation defined as CV hospitalization, unplanned office visits, unplanned remote visits, emergency room visits or death.
- 3. Death

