4.1. SUBJECT POPULATION

The study population will include subjects undergoing catheter ablation of AF with an implanted CIED or indication for CIED that can be implanted prior to randomization per Figure 3.

Consented eligible subjects will be randomized in a 1:1 ratio to either intervention (dapagliflozin 10 mg once daily) or control (placebo); About 13 or 12 subjects enrolled to each group for a total of 25 subjects across all enrolling sites. After enrollment (consent), QoL assessment will be obtained using the AFEQT questionnaire. The subjects will then undergo the index catheter ablation of atrial fibrillation. If CIED does not exist prior to consent then CIED implant will occur prior to, during or within 24 hours of the ablation procedure. Following catheter ablation and successful CIED

implant, the subject will be randomized, baseline data collected and the subject will be followed over a minimum duration of 6 months and up to 12 months duration depending on date of randomization. Subsequent study visits visit will be virtual (through phone contact and/or videoconferencing) in which: a) remote de-identified CIED interrogations will be transmitted to the CDC by the site research coordinator; b) follow-up data on subject status, study drug accountability/compliance, and healthcare utilization/adverse events will be obtained. QoL testing will be repeated at the 12-month follow-up visit. We believe that the virtual approach to study visits and data collection will contribute to significantly higher acceptance and enrollment than in previous studies.

Follow-up visits will be done at 3, 6, 9 and 12 months following randomization.

The study duration is 3 years including a planned study startup period of 6 months, an enrollment period of 18 months, a follow-up period of 6 months, and 6 months for closeout and analysis.

4.2. **STUDY INTERVENTIONS**

Please see section 8 entitled study procedures that includes further study interventions.

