This study is not studying CIEDs nor the AF ablation procedure but will utilize data already clinically used and available from the CIED. Subjects without a CIED in situ will undergo CIED implant at the time of, or within 24 hours following the ablation procedure. All consented subjects will be implanted with a CIED using standard of care procedures and indication and then undergo randomization. All CIEDs including future upgrades that are utilized in this study will be FDA approved and used per the current FDA indications as standard of care to monitor arrhythmias following catheter ablation. Subjects are consented as it is required that the QOL questionnaire be obtained prior to the AF ablation. Subjects will be screen failures and not undergo randomization if catheter ablation is not performed or if there is no existing functional CIED within 24 hours following the ablation procedure.

There are risks associated with the use of any medication. It is important to note that in this study, dapagliflozin will be administered in the intervention according to currently approved FDA indications for it use. Medications inherently may be associated with side effects. The clinical research team is experienced in cardiovascular trials and the clinical management of subjects with heart disease/heart failure and will be monitoring for any adverse effects. This is a Phase 4 study, and we are comparing two management strategies that are currently employed in clinical practice.

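### AFEQT, a secondary endpoint with a required pre-ablation score, is only to be reported as means; a baseline-adjusted difference with a 95% CI would cost almost nothing

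*Combined protocol and SAP*

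**What the plan says.** Section 4 lists secondary endpoint 3 as "AF burden and impact on quality of life measured using the AFEQT score". It gives no time point and no summary measure.

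Section 4.2 explains that subjects consent before the procedure because "it is required that the QOL questionnaire be obtained prior to the AF ablation". A pre-ablation, and therefore pre-randomisation, score should exist for every randomised subject.

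Section 17 gives AFEQT one clause: "mean quality of life AFEQT scores will also be reported". The preceding sentence describes AF burden, health care utilization and HF hospitalization for each group. The t-test is assigned to AF burden. The models are described as follows: "General linear models will be used to identify factors associated with the risk of both AF burden and recurrent endpoints during follow-up". The only stated covariate adjustment is: "We will perform a sensitivity analysis where we adjust for diabetics and heart failure both parametrically and non-parametrically".

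On timing, section 4.1 repeats the quality-of-life assessment at the 12-month visit. Section 8 and Table 1 repeat it at the final follow-up visit, which may be month 6, 9 or 12.

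**The concern.** A listed secondary endpoint has no planned estimate of the treatment difference, and a mandatory baseline measurement enters no analysis. Two arm means leave the reader to form the contrast without its uncertainty. If the form of the contrast (final score, change or adjusted difference) is chosen after unblinding, the choice can be influenced by the data.

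Endpoint 3 can also be read in two ways: as a comparison of arms, or as the association of AF burden with quality of life. Exploratory endpoint 2 uses the second form openly ("Association of AF burden and AF type (paroxysmal vs persistent) with clinical decompensation"). Section 17 analyses neither reading.

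A smaller matter is that sections 4.1 and 8 disagree on when the follow-up questionnaire is given. A questionnaire not given at a subject's last visit cannot be recovered.

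**Working it through.** **Inputs.** From section 17: 25 randomised, 23 evaluable in the power table, 6-month minimum and 9-month average follow-up. From section 4.1: 1:1 allocation, 18 months of enrolment, a further 6 months of follow-up, and a 12-month cap per subject. Assumed: 12 versus 11 evaluable, and r = 0, 0.3, 0.5 or 0.7. The documents give no AFEQT SD, so results are in SD units. They state no AFEQT precision or power figure, so there is none to reproduce.

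**Unadjusted 95% CI half-width.** Standard error factor = √(1/12 + 1/11) = 0.417. Half-width = t(0.975, 21) × 0.417 = 2.080 × 0.417 = 0.87 SD.

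**ANCOVA half-width.** The variance factor, including the price of estimating the slope, is (1 − r²)(N − 3)/(N − 4) = (1 − r²) × 20/19 for N = 23. Half-width = t(0.975, 20) × 0.417 × √factor, with t = 2.086.

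| r | variance factor | half-width (SD) |
|---|---|---|
| 0 | 1.053 | 0.89 |
| 0.3 | 0.958 | 0.85 |
| 0.5 | 0.789 | 0.77 |
| 0.7 | 0.537 | 0.64 |

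The variance breaks even at r = √(1/20) = 0.22. The half-width also carries the slightly larger t quantile, so it breaks even where (1 − r²) × 20/19 = (2.080/2.086)², at about r = 0.24.

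**Coverage.** In simulated 12-versus-11 trials with no true effect, unadjusted and ANCOVA intervals both cover about 95% over all trials. The chance that the arms differ at baseline by more than 0.5 SD is P(|Z| > 0.5/0.417) = 0.23. In those trials unadjusted coverage is about 94%, 89% and 86% at r = 0.3, 0.5 and 0.7. In the other 77% it is about 96%, 97% and 98%. ANCOVA stays near 95% in both groups.

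**Subjects without a follow-up AFEQT if section 4.1 were followed literally.**

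- *Section 4.1 timeline, even accrual assumed.* Subjects randomised in the first 12 of 18 months reach month 12: 25 × 12/18 ≈ 17, so about 8 miss it. Average follow-up is (12 × 12 + 6 × 9)/18 = 11 months. If a visit at month 11 counts (the window is ±1 month), 25 × 13/18 ≈ 18 reach it and about 7 miss it.
- *Section 17 average of 9 months.* Total follow-up is 25 × 9 = 225 months. If k subjects reach month 12 and the rest have at least 6 months, 12k + 6(25 − k) ≤ 225, so k ≤ 12 and at least 13 miss it. Counting month 11, 11k + 6(25 − k) ≤ 225, so k ≤ 15 and at least 10 miss it.

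**The case against.** The strongest reply is that this is a pilot of 25 and that section 17 treats the other two secondary endpoints descriptively as well. That stands, and it is why the recommendation is an estimate with an interval, not a test. A second reply is that r is undocumented and that an ablation between the two questionnaires could weaken it. That also stands: at r = 0.3 the gain is only 0.87 to 0.85 SD, and below about 0.24 the interval is slightly wider.

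A reader might infer more than the documents support:

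- *That unadjusted results would be invalid.* They would not. Coverage is 95% overall, and the shortfall under chance imbalance is offset in the remaining trials.
- *That means would not be given by arm.* The clause follows directly on a sentence about each group, so by arm is the natural reading.
- *That lower-ranked outcomes receive a better analysis.* Section 4 does say that "the following exploratory outcomes will be compared between the two groups", but a descriptive comparison would satisfy that, and section 17 assigns those outcomes no test.
- *That the baseline AFEQT is ambiguous.* Section 4.1 does speak of baseline data after ablation ("the subject will be randomized, baseline data collected and the subject will be followed over a minimum duration of 6 months"), but sections 4.1 and 4.2 both place the questionnaire before ablation, and no competing AFEQT baseline is described.
- *That more than half of the follow-up scores will be lost.* The figure of 13 uses only the 9-month average; the section 4.1 timeline gives about 8. Section 4.2 sends readers to section 8, which with Table 1 governs procedures, so either loss is unlikely.

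**Conclusion.** The point holds as a cheap improvement of minor severity. The plan neither estimates a between-arm AFEQT difference nor uses a baseline score that it requires. Adjustment shortens the 95% CI by roughly 2%, 11% or 27% at r = 0.3, 0.5 or 0.7, and lengthens it by about 3% if r = 0. This rests on 12 versus 11 evaluable subjects and an assumed r. The current plan is not in error statistically, and the primary endpoint is unaffected. The timing conflict is real but mainly editorial.

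**What to change.** **Section 17.** State that the arms are compared on final-visit AFEQT by ANCOVA with the pre-ablation AFEQT as the single covariate, among subjects with a final-visit score. Report the adjusted difference with a 95% CI and make no power claim. Tabulate the final-visit month (6, 9 or 12) by arm. State that this is the analysis of endpoint 3; if an association of AF burden with quality of life is also intended, list it separately.

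**Section 4.1.** Change the repeat quality-of-life assessment from the 12-month visit to the final follow-up visit, matching section 8 and Table 1.

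**Cost.** A few sentences and one degree of freedom; no new visit, questionnaire or subject. Section 17 already refers to enrolled patients, so make the change before unblinding and confirm the AFEQT time point with the sites.

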8. STUDY PROCEDURES

After signing consent, all subjects will undergo randomization and study related procedures, as well as standard of care procedures, per Table 1 and as indicated below.

All subjects will either have a functional CIED already implanted prior to AF ablation, at time of AF ablation or within 24 hours following AF ablation as standard of care.

All subjects enrolled in the study will remain on SOC medications and participation in the study will not require discontinuation of any SOC medications.

Intervention Management Arm (Dapagliflozin)

A block randomization method will be use to randomize subjects to treatment with dapagliflozin 10 mg once daily versus placebo. Subjects will take 1 blinded tablet of study drug (dapagliflozin) dosed once daily, per the randomization scheme, for a 6-12 month duration depending on date of randomization. All active and placebo tablets will be identical in appearance (same size, shape and color). Subjects will be encouraged to start study drug within 2 weeks of the date of randomization. Study subjects will be instructed to ingest all tablets whole and not to open them. Each subject will be dispensed 35 blinded doses per month, during each month of participation in the trial. Quarterly pill counts will be performed to track compliance. All drug dispensing (dapagliflozin and matching placebo) will be managed by the Investigational Drug Services (IDS) in the Department of Pharmacy at the University of Rochester Medical Center. The unit manages drug dispensing for numerous clinical trials and

has vast experience in this field. Any study related side effects will be reported to the independent Data and Safety Monitoring Board (DSMB) for review (details below). The cost of study drug will be covered by the study.

Patients with diabetes who are started on dapagliflozin will continue to undergo standard of care glucose monitoring as directed by the primary treating physician. The initiation of dapagliflozin does not require any incremental testing/monitoring beyond what is performed as standard of care.

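### AF type structures enrolment and is expected to drive AF burden, yet neither the primary t-test nor the sensitivity analysis includes it

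*Combined protocol and SAP*

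**What the plan says.** All of the following is in the combined protocol and SAP.

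- **Enrolment.** Section 17 states that "enrollment will use a stratified proportionate allocation in a 2:1 ratio by type of AF", persistent to paroxysmal, so that enough persistent subjects are included.
- **Why AF type matters.** Section 17 describes an in-house series of 125 monitored patients, "of whom 65% had persistent AF, show an overall AF burden of 25" percent, and adds: "Other published studies have shown a higher burden of AF in persistent AF populations".
- **Primary comparison.** Section 17: "the student's t-test will be used to statistically compare the placebo group vs. the active treatment group". The only qualification is "This approach is subject to an examination of the distribution of the percent time in AF".
- **Sensitivity analysis.** Section 17, under Sample size: "We will perform a sensitivity analysis where we adjust for diabetics and heart failure both parametrically and non-parametrically". AF type is not named.
- **Other modelling.** Section 17: "General linear models will be used to identify factors associated with the risk of both AF burden and recurrent endpoints during follow-up". No covariates are listed.
- **Randomization.** Section 8: "A block randomization method will be use to randomize subjects". No strata are given there or under the method of assigning treatment.

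AF type otherwise enters the planned analyses only as an exploratory association with clinical decompensation (Section 4, tertiary endpoints).

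**The concern.** AF type is the only stratification factor the documents name, and the plan treats it as prognostic for the primary endpoint. Leaving it out of the treatment comparison has a cost under either reading of the allocation text.

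If the 2:1 rule governs only who is enrolled, the arms can differ by chance in their share of paroxysmal subjects. The t-test would carry that imbalance straight into the estimate. If the rule also means that randomization is stratified by type, the design removes the between-type variation from the treatment difference, but the t-test leaves it in the error term. The test is then conservative and loses power.

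The sample size is fixed at 25, so the analysis is the main means left of gaining precision. Without adjustment, an effect of the planned size is easier to miss than it need be, and a difference created or masked by an uneven split of AF type would stand uncorrected.

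**Working it through.** **Inputs from Section 17.** 25 randomized; 10% dropout; SD 15 points; placebo burden 40%; dapagliflozin 20, 22, 22.8 or 24%; 2:1 persistent to paroxysmal. Section 4.1 gives arms of 13 and 12.

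**Assumptions.** Two-sided 5% test; normal data; 8 paroxysmal subjects among 25 randomized and among 22 evaluable; a gap in mean burden between types of 0 to 30 points. The documents give no gap. The in-house series bounds it in that population only: if persistent is the higher group and paroxysmal burden were zero, persistent burden would be 25 / 0.65 = 38.5%, so the gap cannot exceed 38.5 points.

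**Step 1: the plan's own power.** Noncentral t, 11 per arm, 20 degrees of freedom, noncentrality = difference / (15 × √(2/11)) = difference / 6.396. Differences of 20, 18, 17.2 and 16 points give 84.5, 76.3, 72.5 and 66.3%, against 85, 76, 73 and 66% stated. The table is therefore an unadjusted t-test calculation. (It lists 23 evaluable; 11 versus 12 gives 86.1, 78.3, 74.5 and 68.3%, a slightly worse match.)

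**Step 2: chance imbalance if randomization is not stratified.** The number of paroxysmal subjects in the arm of 13 is hypergeometric (8 of 25). Shares differ by 25 points or more when the split is 6/2 or 2/6 or more extreme:

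- at least 6 in the arm of 13: (113,256 + 20,592 + 1,287) / 1,081,575
- at most 2 in the arm of 13: (72,072 + 10,296 + 495) / 1,081,575
- total: 217,998 / 1,081,575 = 0.202

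The 6/2 split gives 6/13 − 2/12 = 0.295; the 2/6 split gives 6/12 − 2/13 = 0.346. At a 20-point gap these shift the treatment difference by 5.9 and 6.9 points, against a planned effect of 16 to 20.

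**Step 3: the two readings of the SD.** Between-type SD in a 2:1 mix = gap × √(2/9), which is 4.7, 9.4 and 14.1 at gaps of 10, 20 and 30.

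- If 15 is within type, the overall SD is √(15² + between²) = 15.7, 17.7 and 20.6.
- If 15 is overall, the within-type SD is √(15² − between²) = 14.2 and 11.7 at gaps of 10 and 20.

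**Step 4: power by simulation, randomization not stratified.** 60,000 trials per scenario, 11 per arm. Entries are t-test / adjusted for AF type, in percent.

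| Gap | 40 vs 20, SD 15 within type | 40 vs 24, SD 15 within type | 40 vs 20, SD 15 overall | 40 vs 24, SD 15 overall |
|---|---|---|---|---|
| 0 | 84.7 / 82.4 | 66.0 / 63.7 | as within type | as within type |
| 10 | 80.8 / 82.4 | 61.7 / 63.5 | 84.3 / 86.1 | 66.1 / 68.4 |
| 20 | 70.1 / 82.7 | 51.0 / 63.9 | 83.1 / 95.8 | 64.4 / 84.2 |
| 30 | 55.9 / 82.3 | 38.9 / 63.5 | not run | not run |

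With 12 versus 11 and SD 15 within type, 40 vs 20 gives 86.2/84.2, 82.5/84.2, 72.4/84.2 and 58.0/84.1 at gaps of 0, 10, 20 and 30.

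**Step 5: randomization stratified by type (4 paroxysmal per arm), gap 20.** The t-test's true type I error is 2.0% (SD 15 within type) or 1.0% (overall); the adjusted model holds 4.9 to 5.0%. Power for 40 vs 20 is 72.6/84.2 or 88.5/96.7. At gap 0 it is 84.3/84.1, so adjustment then costs 0.2 points.

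**Step 6: less favourable cases, not stratified, gap 20.** If treatment halves burden within each type rather than subtracting a constant, power is 73.9/81.1 (within type) or 82.7/90.3 (overall). With bounded, skewed (beta-distributed) burden, halving in each type, SD 15 within type and 12 versus 11, the figures are: t-test 74.2, adjusted model 81.4, Wilcoxon 71.2, van Elteren 80.2. At gap 0 the same four are 83.8, 81.8, 83.2 and 80.4.

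**The case against.** The strongest objection concerns the SD. The power table enters 15 directly into an unadjusted two-arm calculation, where it most naturally means the spread of all subjects in an arm. AF-type variation is then already counted, the t-test delivers 83 to 84% against the stated 85% for 40 vs 20, and adjustment is a bonus rather than the repair of a shortfall. This stands as a limit: the 70, 56, 51 and 39% figures need 15 to be the within-type SD, and the plan does not say which it is. The gain forgone at a 20-point gap is still about 13 points on the overall reading.

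The gap itself is unknown, and large gaps strain an additive normal model for a 0 to 100% endpoint. With 40 vs 20 and a 20-point gap, treated paroxysmal subjects average 20 − (14/22) × 20 = 7.3%, and 27 to 31% of the modelled values fall below zero. This also stands. The proportional and bounded checks bring the gain down to about 7 or 8 points. With overall SD 15, break-even lies between gaps of 5 and 10 points.

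The t-test is valid without stratification: its type I error stays near 5%, because chance imbalance is part of the error it allows for. That is correct. The issue is precision and the realised imbalance, not validity.

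The general linear models might include treatment and AF type. They might, but they are described as a search for associated factors and name no covariates, so they do not specify an adjusted treatment comparison.

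The adjustment set has a rationale, since Section 17 links the higher burden to heart failure, diabetes and renal dysfunction. That explains the factors chosen; it does not explain omitting the one used to structure enrolment.

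Finally, Section 17 calls the results pilot data, and preliminary device interrogations have already informed the re-estimate. The same section makes explicit power claims, and a pilot estimate also benefits from less noise. The earlier look at data is a reason to document the timing of any change carefully.

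**Conclusion.** The concern holds and should be fixed. The plan enrols by AF type, expects it to affect burden, and then omits it from both the primary test and the only specified adjusted analysis.

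The size is conditional on the unstated gap between types. Adjustment costs about 2 points of power at zero gap (0.2 if randomization is stratified) and adds about 2 points at a gap of 10 in unstratified designs. At a gap of 20 it adds roughly 7 to 20 points, depending on the SD reading, the planned effect and whether the effect is additive or proportional. Separately, there is a 20% chance of a marked imbalance in AF type if randomization is unstratified. If it is stratified, the t-test's true type I error is 1 to 2% at a gap of 20.

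These figures rest on a two-sided 5% test and 22 evaluable subjects, mostly with normal outcomes. Confidence is medium because the gap and the meaning of the SD are not documented.

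**What to change.** Before unblinding, in a dated amendment:

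1. Make the primary comparison a linear model of AF burden on treatment and AF type as recorded at enrolment, reporting the adjusted difference with its 95% confidence interval. Keep the unadjusted t-test as a sensitivity analysis.
2. State that if the distribution check rules out normal-theory methods, a rank test stratified by AF type (van Elteren) replaces the linear model.
3. Add AF type to the sensitivity model alongside diabetes and heart failure.
4. State whether randomization is stratified by AF type, and whether the 15% SD is within type or across all subjects.

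The cost is one degree of freedom and about 2 points of power if AF type turns out to be unrelated to burden. AF type must already be recorded to run the 2:1 enrolment, so no subjects, visits or endpoints are added. Because some interrogation data have already been reviewed, the amendment should record what had been seen and that treatment assignment remained blinded when the change was made. If AF type were added only after an imbalance had been seen, the change would be open to challenge as data-driven.
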